5.1 Inclusion criteria

Participants eligible for inclusion in this study must meet **all** of the following criteria:

- 1. Signed informed consent must be obtained prior to participation in the study.
- 2. Male and female participants 18 years or older (at the time of the screening visit)
- 3. Presence of NASH with fibrosis confirmed by central reader's evaluation of liver biopsy obtained no more than 6 months before randomization as demonstrated by the following:
 - a. NASH using NAFLD Activity Score (NAS) ≥ 4 with at least 1 point each in inflammation and ballooning on the screening histology assessment performed by the central reader

and

- b. Fibrosis stage 2 or 3 using NASH CRN fibrosis criteria (see Table 8-2 & Table 8-3)
- 4. Able to communicate well with the investigator, to understand and comply with the requirements of the study

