5.2 Exclusion criteria

Participants meeting any of the following criteria are not eligible for inclusion in this study.

- 1. Taking medications prohibited by the protocol. (see Section 6.2.2, Table 6-3)
- 2. Pregnant or nursing (lactating) women.
- 3. Weight at Baseline changed by > 5% since qualifying liver biopsy.
- 4. History of hypersensitivity to either of the study drugs or their excipients or to drugs of similar chemical classes, or participants with hereditary galactose intolerance, lactase deficiency or glucose-galactose malabsorption.
- 5. Taking a permitted medication listed in Table 6-2 but who is NOT on a stable dose (within 25% of Baseline dose) from the start of the screening period and
 - a. for at least 3 months prior to the Baseline visit for thyroid hormone, oral antidiabetic medication, insulin, GLP-1 agonists, and estrogen or estrogen containing birth control
 - b. for at least 6 months prior to Baseline for Vitamin E
- 6. Current, or history of, significant alcohol consumption for a period of more than 3 consecutive months within 1 year prior to screening.
 - a. Significant alcohol consumption is defined as more than 20 g/day (14 units/week) in females, or more than 30 g/day (21 units/week) in males, on

Novartis	Confidential	Page 73 of 160
Amended Protocol Version 02 (Clean)		Protocol No. CLJN452D12201C

average. A "unit" of alcohol is equivalent to one (12-ounce; 355 ml) beer, one glass (4-ounce; 120 ml) of wine, or 1 shot (ounce; 30 ml) of hard liquor.

or

- b. A score on the alcohol use disorders identification test (AUDIT) questionnaire ≥ 8 .
- 7. Diabetes related:
 - a. Type 1 diabetes mellitus.
 - b. Uncontrolled type 2 diabetes defined as $HbA1c \ge 9.0\%$ at screening.
 - c. HbA1c < 6.5% at screening in Type 2 diabetics currently treated with insulin or sulfonylureas.
- 8. Platelet count < LLN (see Central laboratory manual).
- 9. Clinical evidence of liver impairment as defined by the presence of any of the following abnormalities:
 - a. Serum albumin < LLN (see Central laboratory manual).
 - b. International Normalized Ratio (INR) > ULN (see Central laboratory manual).
 - c. ALT or $AST > 5 \times ULN$ (in either of the 2 values during screening).
 - d. Total bilirubin > ULN (see Central laboratory manual) (in either of the 2 values during screening), including Gilbert's syndrome.
 - e. Alkaline phosphatase > 300 IU/L (in either of the 2 values during screening).

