- 23. Symptomatic genital or urinary tract infection within 4 weeks prior to randomization or participants with high risk as, determined by the investigator (including concomitant therapy with immunosuppressive potential), to be particularly susceptible to genital or urinary tract infection.
- 24. Recent history of gastrointestinal disorder associated with chronic diarrhea.
- 25. Any history of and/or suspected Fournier's gangrene, or participants with high risk as, determined by the investigator (including concomitant therapy with immunosuppressive potential), to be particularly susceptible to Fournier's gangrene.
- 26. Diabetic foot ulcer within 4 weeks prior to randomization.
- 27. History of inflammatory bowel disease (ulcerative colitis, Crohn's disease).
- 28. Known positivity for Human Immunodeficiency Virus (HIV) infection. HIV antigen/antibody tests will be performed to determine HIV status if allowed and required according to local regulations.
- 29. History of malignancy of any organ system (other than localized basal cell carcinoma of the skin or in situ cervical cancer), treated or untreated, within the past 5 years, regardless of whether there is evidence of local recurrence or metastases.
- 30. History or evidence of ongoing drug abuse, within the last 6 months prior to randomization.
- 31. Use of other investigational drugs within 5 half-lives of randomization, or within 30 days, whichever is longer.

- 32. Previous exposure to any other investigational or recently (2019 onwards) approved NASH treatment within 6 months prior to qualifying biopsy (participants known to have only received placebo may be included).
- 33. Sexually active males must use a condom during intercourse while taking drug and for 5 days after stopping investigational medication and should not father a child in this period. A condom is required to be used also by vasectomized men in order to prevent delivery of study drug via seminal fluid. (With-amendment version 01, this exclusion criterion is no longer applicable).
- 34. Women of child-bearing potential, defined as all women physiologically capable of becoming pregnant, unless they are using highly effective methods of contraception during dosing and for 5 days (> 5 times the terminal half-life) after stopping of investigational medication. Highly effective contraception methods include:

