6.2.1 Concomitant therapy

The investigator must instruct the participant to notify the study site about any new medications he/she takes after the participant is enrolled into the study.

All medications, vaccines, procedures, and significant non-drug therapies (including physical therapy and blood transfusions) administered after the participant was enrolled into the study must be recorded on the appropriate case report forms (CRF).

Each concomitant drug must be individually assessed against all exclusion criteria/prohibited medication. If in doubt, the investigator should contact the Novartis medical monitor before randomizing a participant or allowing a new medication to be started. If the participant is already enrolled, contact Novartis to determine if the participant should continue participation in the study. There are no restrictions related to COVID-19 vaccines, and these are allowed throughout study participation as permitted by local regulations.

Drugs to control medically significant lipid abnormalities (which have been confirmed upon repeat testing) can be prescribed according to local standard of care. Participants on medications specified in Table 6-2 can be included if these medications are medically necessary, and the investigator feels the dose will remain stable for the duration of the double-blind treatment period. In addition, doses of oral anti-diabetic medication, insulin, GLP-1 agonists, thyroid hormone, and estrogen or estrogen containing birth control, must be stable for at least 3 months prior to the Baseline visit. Sliding scale insulin therapy is allowed if this approach has been implemented for at least 3 months prior to the Baseline visit. Insulin dose adjustment is permitted during the study if required. Doses of vitamin $E \leq 800$ IU/day must be stable for at least 6 months prior to the Baseline visit. A stable dose is defined as a dose within 25% of the Baseline dose. New use or dose adjustments > 25% of the Baseline dose of these medications is not allowed after entering the study.

Table 6-2	Medications permitted only if dose is stable (within 25 percent of
	Baseline dose) and expected to remain stable through the double-
	blind treatment period

Medication	Stable dose start
Oral anti-diabetic medications	At least 3 months prior to the Baseline visit
Insulin	At least 3 months prior to the Baseline visit

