Such as: e.g. erythromycin, metoclopramide, tegaserod, methylnaltrexone, alvimopan, loperamide, diphenoxylate and atropine (Lomotil) and difenoxin and atropine (Motofen))	
Non-selective UGT inhibitors:	Stop at or before Baseline
Such as: diclofenac, probenecid, valproic acid	
Strong CYP3A4 inhibitors:	Stop at or before Baseline
Such as: viekira Pak, indinavir/ritonavir, tipranavir/ritonavir, ritonavir, cobicistat (GS- 9350) ,indinavir, ketoconazole, troleandomycin, telaprevir, danoprevir/ritonavir, elvitegravir/ritonavir, saquinavir/ritonavir, lopinavir/ritonavir, itraconazole, voriconazole,mibefradil, LCL161, clarithromycin, posaconazole, telithromycin, grapefruit juice, conivaptan, nefazodone, nelfinavir, saquinavir, idelalisib, boceprevir, darunavir/ritonavir.	
Strong CYP3A4 inducers:	Stop at or before Baseline
Such as: avasimibe, carbamazepine, phenytoin, rifampin, St. John's wort (Hypericum perforatum), rifabutin, phenobarbital, mitotane, enzalutamide.	
Methotrexate	Stop at least 3 months prior to Baseline
Vitamin E doses > 800 IU/day	Stop (or reduce dose) at least 6 months prior to Baseline
Drugs approved in any market for treatment of NASH	Stop at least 6 months prior to Baseline
Alternative Liver Protection medication:	Stop at or before Screening Visit 1
Silymarin; Bicyclol; Polyene Phosphatidylcholine (Essentiale); Diammonium Glycyrrhizinate; Reduced glutathione (GSH); S- adenosylmethionine–methionine; Ursodeoxycholic Acid (UDCA)	

Table 6-3Prohibited medications

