 - b. Whether the participant has resolution of NASH (absence of ballooning with no or minimal inflammation by histology) and no worsening of fibrosis at week 48 compared with baseline.
- 4. Summary measure: Odds ratio of participants achieving histological response at Week 48 for the following comparisons for each primary endpoint: combination vs. placebo, monotherapies vs. placebo, and combination vs. monotherapies.
- 5. Intercurrent events include
 - > Early discontinuation of study treatment before week 48 visit.
 - Non-histologic clinical event suggesting treatment failures (e.g bariatric surgery, liver transplant and death due to disease).
 - > Study treatment incompliance defined as relative dose intensity >1.25 or <0.75.
 - More than four weeks of cumulative exposure to any prohibited medications Section 6.2.2, alcohol usage more than what is permitted in the protocol, initiation of other T2DM or lipid lowering medication (e.g. GLP-1 modulator, statins), initiation of other treatment being evaluated or approved for NASH, or new concomitant interventions for weight control before the assessment for primary endpoint. The identification of relevant medications will be based on ATC3 and/or ATC5 codes, which will be included in analysis data set specifications. The list of concomitant interventions with significant effect for general weight loss will be determined based on blinded review of the study data.

For the intercurrent events related to the primary estimand, various strategies (such as treatment policy and composite variable) defined in ICH E9 (R1) will be utilized for the analyses. For instance, participants who discontinue the treatment after Week 24 will be asked to have their biopsies assessed at Week 48 regardless of the intercurrent event (treatment policy strategy), participants who discontinue the treatment before Week 24 will be considered as non-responders (composite variable strategy), and participants who have no biopsies extracted at Week 48 will be considered as non-responders (composite variable strategy).

Novartis	Confidential	Page 135 of 160
Amended Protocol Version 02 (Clean)		Protocol No. CLJN452D12201C

For non-intercurrent event missing data, certain multiple imputation methods will be applied to estimate the endpoints.

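### Exclusion 32 stops at the qualifying biopsy, so an investigational NASH drug can be taken between the baseline biopsy and the short pre-randomization washout without breaching any listed criterion

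*Protocol*

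**What the plan says.** - **Age of the baseline biopsy.** Inclusion criterion 3 (Protocol 5.1) accepts a "liver biopsy obtained no more than 6 months before randomization". Sections 8.1.1 and 8.1.2 expect some of these biopsies to be historical.
- **Role of the biopsy.** Protocol 12.4.1 scores both primary endpoints as change from baseline to Week 48. SAP 2.1.1 defines baseline as the last valid assessment before first dose, which for histology is the qualifying biopsy.
- **Criterion 32 (5.2).** It excludes "Previous exposure to any other investigational or recently (2019 onwards) approved NASH treatment within 6 months prior to qualifying biopsy". The window runs backwards from the biopsy.
- **Criterion 31 (5.2).** It excludes "Use of other investigational drugs within 5 half-lives of randomization, or within 30 days, whichever is longer". The window runs backwards from randomization.
- **Table 6-3 (6.2.2), enforced by criterion 1.** It lists "Drugs approved in any market for treatment of NASH", to be stopped at least 6 months before Baseline. Investigational NASH agents have no row.
- **Permitted drugs (criterion 5, 6.2.1, Table 6-2).** Antidiabetics, insulin and GLP-1 agonists "must be stable for at least 3 months prior to the Baseline visit", and must also be stable from the start of screening. Vitamin E has a 6-month window.
- **After treatment starts.** Section 12.4 names "initiation of other treatment being evaluated or approved for NASH" as an intercurrent event.

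**The concern.** A washout rule protects a change-from-baseline endpoint only if it covers the time when the baseline is measured and the time from there to randomization. Criterion 32 protects the histology up to the biopsy and then stops. Criterion 31 takes up again only shortly before randomization. A NASH-active investigational drug taken in between could alter the liver after the baseline was fixed. Any resulting change would be scored at Week 48 as response, or would hide one, whatever the assigned arm.

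Sites cannot close the gap on their own. Section 5 tells investigators not to add criteria, and criterion 35 reaches only conditions that would impair compliance or completion. The instruction in 6.2.2 to stop drugs once screening is considered applies to the drugs in Table 6-3. Nor is such exposure an intercurrent event, because it comes before treatment starts.

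**Working it through.** **1. Length of the gap.** Uncovered days = max(0, longest biopsy-to-randomization interval − look-back window). Inputs:
- historical biopsy: 6 months × 30.44 = 183 days (5.1)
- biopsy at the start of screening: 10 weeks = 70 days (8.2.1)
- criterion 31: 30 days, assuming 5 half-lives do not exceed 30 days, that is, a half-life of at most 6 days
- 3-month rows: 91 days; 6-month rows: 183 days.

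| Drug class | Historical biopsy | Screening biopsy |
|---|---|---|
| Investigational NASH drug | 183 − 30 = 153 | 70 − 30 = 40 |
| Approved NASH drug, vitamin E (6 months) | 183 − 183 = 0 | 0 |
| Antidiabetics, insulin, GLP-1 agonists, SGLT2 inhibitors, weight-loss drugs, methotrexate (3 months) | 183 − 91 ≈ 91 (unrounded months) | 0 |

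A longer half-life shortens the first row.

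**2. Worked case.** Biopsy on day −180; investigational NASH drug with a half-life under 8 days on days −170 to −40.
- Criterion 32: exposure is after the biopsy, so it is not caught.
- Criterion 31: 5 × 8 = 40 days, so the last dose lies outside the window.
- Table 6-3: the drug is not approved, so it is not listed.

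The participant is eligible on all three.

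**3. Effect on power.** Inputs are the Table 12-3 rates (fibrosis 35% vs 20%, NASH resolution 25% vs 10%), n = 140 and 80, endpoint correlation +0.5, and two-sided 2.5% per endpoint (critical value 2.241). The test is z = (p1 − p2) / √[p1(1 − p1)/140 + p2(1 − p2)/80]. Simulation gives 0.85 for winning on at least one endpoint, which matches Table 12-5. The single-endpoint values are 0.61 and 0.77.

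Now let a fraction f of participants have their response probability shifted by δ, so each rate becomes p + fδ. The documents give neither f nor δ; both are assumptions.

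| f | Shift δ | Fibrosis rates | NASH rates | Power, at least one |
|---|---|---|---|---|
| 5% | placebo +10, combination +5 points | 35.25 vs 20.5 | 25.25 vs 10.5 | 0.83 |
| 10% | same | 35.5 vs 21 | 25.5 vs 11 | 0.81 |
| 5% | +10 points in both | 35.5 vs 20.5 | 25.5 vs 10.5 | 0.84 |
| 10% | same | 36 vs 21 | 26 vs 11 | 0.83 |

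Reversing the sign of δ raises power slightly instead: with −10 points in both arms, 0.86 at either f.

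**The case against.** Most of the case against a broader claim stands.

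- **Approved NASH drugs have no gap.** Exclusion applies if any criterion is met, so criterion 32 and Table 6-3 add up. With a biopsy at month −6, criterion 32 covers months −12 to −6 and Table 6-3 covers month −6 to Baseline. A reader might infer that the two rules conflict (12 months against 6); they are cumulative.
- **Not every window runs from Baseline.** Criterion 5 also requires stability from the start of screening, and several rows of Tables 6-2 and 6-3 are tied to Screening Visit 1.
- **The 3-month rows look like a considered choice.** They leave a gap only when the biopsy is more than 3 months old. The Amendment 01 summary records that the FDA requested the 3-month antidiabetic window and the 6-month vitamin E window before Baseline, and that a biopsy-anchored stability rule was dropped in the same change. The primary estimand also disregards later antidiabetic changes (2.1, 12.4.3). Re-anchoring these rows is a trade-off, not a correction.
- **Direction is not established.** In the worked case the effect would have to last from day −40 to day 336, or 376 days off drug. A drug in use at the biopsy and then stopped could lower later response. The planned placebo rates (20% and 10%) already exceed the published ones in Table 12-2 (at most 17.5% and 9%).
- **Other safeguards.** Criterion 3 limits weight change since the biopsy to 5%, which catches some weight-active exposure. Section 8.3.1.8, on biopsy details, is not legible in the public text, so a further rule there cannot be ruled out.

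None of this covers an investigational NASH drug taken after the biopsy.

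**Conclusion.** The point holds for investigational NASH drugs: up to about 5 months between the baseline biopsy and randomization are uncovered with a historical biopsy, and about 40 days with one taken at the start of screening. It rests on the legible text and on a half-life of 6 days or less for the full gap.

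Two stronger readings are not supported. One is that any NASH-active drug can slip through; approved NASH drugs and vitamin E cannot. The other is that the gap biases the treatment comparison or must raise placebo response. The exposure precedes randomization, so it is non-differential between arms in expectation, and its sign is unknown.

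The likely cost is small: at-least-one-endpoint power of 0.85 falling to about 0.81-0.84 under the unfavourable shifts, with an assumed 5-10% affected. The documents do not say how many biopsies are historical or how many participants had such exposure. The loss is roughly proportional to that share. The point is worth acting on because the change is nearly free, not because the trial is at risk.

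**What to change.** 1. **Criterion 32.** Reconcile it with criterion 31 and with the use of the biopsy as baseline: keep its 6-month look-back and let the exclusion run on through the qualifying biopsy until randomization.
2. **Participants already randomized.** Before unblinding, flag post-biopsy exposure to investigational NASH drugs from the prior-medication eCRF (8.2.6), and repeat the analysis of both primary endpoints without those flagged. Use medical review as well as ATC codes, since an investigational agent may have no code. The flag is fixed before randomization, so the remaining comparison is still randomized.
3. **The 3-month rows.** No new window is proposed. Post-biopsy starts, stops or changes of those drugs can be flagged in the same sensitivity analysis.

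Cost: one line of eligibility wording at the next amendment and one added analysis in the SAP. A few participants could not enter on a historical biopsy. No extra procedure or visit is needed.

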6.1 Study treatment

6.1.1 Investigational and control drugs

The 140 μ g dose of tropifexor and its matching placebo are each now available as a single hard gelatin capsule. Participating at the time of availability of the single tropifexor/placebo capsule, may continue on the 3-capsule tropifexor (100 μ g + 30 μ g + 10 μ g) or matching placebo regimen described in protocol v01 until the available 3-capsule supply is depleted. After the 3-capsule supply is depleted, participants will take one 140 μ g tropifexor or matching placebo capsule daily as described in Table 6-1. See Sections 6.1.3 and Section 6.7.2 for additional information regarding tropifexor dosing utilizing the 3 capsule and single capsule regimens. No change has been made to licogliflozin dosing.

Investigational/ Control Drug (Name and Strength)	Pharmaceutical Dosage Form	Route of Administratio n	Presentation Type	Sponsor (global or local)
Tropifexor (LJN452) 140 μg	140 μg hard gelatin capsule	Oral	Double blind	Novartis (global)
Placebo Tropifexor (LJN452) 140 μg	Hard gelatin capsule matching to tropifexor (LJN452) 140 µg	Oral	Double blind	Novartis (global)
Licogliflozin (LIK066) 30 mg	10 mg film coated tablets	Oral	Double blind	Novartis (global)
Placebo Licogliflozin (LIK066) 30 mg	Film coated tablets matching to licogliflozin (LIK066) 10 mg	Oral	Double blind	Novartis (global)

 Table 6-1
 Investigational and control drug

6.1.2 Additional study treatments

No other treatment beyond investigational drug and control drug are included in this trial.

An overview of the prohibited medication is given in Table 6-3, and the summary of permitted medication if on stable dose is in Table 6-2.

6.1.3 Treatment arms/group

Participants (n = 380) will be assigned at Baseline visit to one of the following 4 treatment arms in a ratio of 1.75:1:1:1 in a blinded manner. Placebo capsules/tablets will be given in each treatment arm where necessary to maintain blinding.

Arm A: Combination therapy Arm - (N=140): tropifexor 140 μ g + licogliflozin 30 mg, once daily.

Arm B: Tropifexor monotherapy Arm - (N=80): tropifexor 140 μ g (+ placebo matching licogliflozin), once daily.

Arm C: Licogliflozin monotherapy Arm - (N=80): licogliflozin 30 mg (+ placebo matching tropifexor), once daily.

Arm D: Placebo Arm – (N=80): placebo matching tropifexor + placebo matching licogliflozin, once daily.

The 140 μ g dose of tropifexor and its matching placebo are each now available as a single hard gelatin capsule. Participants participating at the time of availability of the single tropifexor/placebo capsule, may continue on the 3-capsule tropifexor (100 μ g + 30 μ g + 10 μ g) or matching placebo regimen until the available 3- capsule supply is depleted. After the 3-capsule tropifexor or matching placebo supply is depleted, participants will take one 140 μ g tropifexor or matching placebo capsule daily. No change is made to licogliflozin dosing. Further details can be found below and in Section 6.7.2.

6.1.3.1 Dosing with 3 capsule $(10 + 30 + 100 \mu g)$ tropifexor supply

Until 3-capsule tropifexor ($100 \ \mu g + 30 \ \mu g + 10 \ \mu g$) and matching placebo is replaced by the 140 μg hard gelatin single capsule, in order to maintain the blind, placebo capsules matching tropifexor (LJN452) 10, 30 and 100 μg and placebo tablets matching licogliflozin (LIK066) 10 mg will be given to participants as indicated in Table 6-5, so that all participants will receive 3 capsules and 3 tablets per day. **One capsule from each of the 3 bottles**, and **3 tablets from the blister pack** should be taken close to the evening meal; either just prior to (within 5 minutes) consuming the evening meal, or no more than 30 minutes after consuming the evening meal and at about the same time each day.

